11.8 Mechanical Ventilation Status

If the patient is receiving invasive mechanical ventilation, ventilatory parameters will be collected daily between 06:00 and 10:00, including the following, per local procedure:

Mode of ventilation, FiO₂(Fraction of inspired oxygen), SpO₂ , plateau pressure, peak pressure, PEEP (Positive End-Expiratory Pressure). If an ABG (arterial blood gas) is obtained during that time, then the PaO₂ (Partial pressure of arterial oxygen) will also be collected.

If the patient is receiving non-invasive ventilation, the level of inspiratory pressure, FIO₂, and PEEP will be registered. If the patient is receiving high-flow oxygen, the flow rate and the FIO₂ will be recorded.

The proportion of subjects requiring mechanical ventilation will be assessed on Study Days 7, 14, 21, and 28, and the number of days free of mechanical ventilation will be assessed on Days 28 and 56.

11.9 Chest Imaging

Radiograph or CT imaging will be performed as scheduled in the SOE to the extent feasible. Subjects who are ambulatory and discharged from hospital may forego further imaging if impracticable without incurring a protocol deviation.

11.10 Clinical Laboratory Tests

Blood and urine samples will be collected according to the SOE and below. All laboratory tests will be performed at the local laboratory. Samples will be collected pre-dose on Day 0 as per SOE. Repeat laboratory testing will not be required if a test was already performed within the specified time window for collection. Samples may be analyzed for the tests outlined in this protocol and for any additional tests (with the Sponsor's approval) necessary to further evaluate subject safety. These may include, but are not limited to, investigation of unexpected results. Subjects will be in a seated, semi-recumbent, or supine position during blood collection. Collection procedures are described in the study Laboratory Manual.

Table 3 presents the clinical laboratory assessments to be performed.

Table 3. Clinical Laboratory Parameters

Chemistry	Hematology	Urinalysis	Viral Studies

 Sodium Potassium Chloride Bicarbonate Calcium Magnesium Phosphorus Glucose BUN Creatinine Total protein Albumin Uric acid LDH Total bilirubin Direct bilirubin Indirect bilirubin Alkaline phosphatase ALT AST GGT 	
 RBC count Hgb Hct Platelet count WBC count with differential: neutrophils, lymphocytes including absolute CD4 and CD8 count, monocytes, eosinophils, and basophils (absolute counts and percentages) 	
 Appearance Color Specific gravity pH Blood Protein Glucose Bilirubin Urobilinogen Leukocyte esterase Nitrite 
Microscopic analysis:
 
 WBC RBC Epithelial cells Bacteria Casts and/or crystals^a 	
 Anti-HIV Ab HBsAg Anti-HCV Ab (if positive, HCV RNA will be measured) 
Other
 
 Urine pregnancy test^b Ferritin C-reactive protein d-dimer high-sensitivity troponin

Abbreviations: ALT = alanine aminotransferase; AST (SGOT) = aspartate aminotransferase; BUN = blood urea nitrogen; GGT = gamma-glutamyl transferase; HBsAg = hepatitis B surface antigen; Hct = hematocrit; HCV = hepatitis C virus; Hgb = hemoglobin; HIV = human immunodeficiency virus; LDH = lactate dehydrogenase; RBC = red blood cell; RNA = ribonucleic acid; WBC = white blood cell

^a Microscopic analysis of urine should only be performed if clinically indicated.

^b Pregnancy testing only for women of childbearing potential.

11.11 Exploratory Pharmacokinetic and Pharmacodynamic Biomarkers

Table 4 summarizes laboratory mechanistic analyses for assessing PK and PD of cePolyTregs using samples collected as described in the SOE.

Table 4. Mechanistic Assessments of cePolyTregs PK and PD

PK Markers
Change from baseline in circulating cePolyTregs
Change from baseline in pulmonary cePolyTregs by endotracheal aspirate and mini BAL
cePolyTregs expansion and activation using scRNA/TCR-sequencing
PD Markers
Change from baseline in acute phase reactants, e.g. ferritin, C-reactive protein, LDH, and albumin
Change from baseline in endothelial cell injury markers, e.g. d-dimer, soluble thrombomodulin, VWF, and angiopoietin-2
Change from baseline in lung epithelial cell and other tissue injury markers, e.g. RAGE, KL-6, SF-D, and troponin I
Change from baseline in absolute lymphocyte count
Change from baseline in inflammatory markers, e.g. IL-6, IL-12, IFN γ , GM-CSF, TNF α , IP10, MCP-1, MCP3, C3, C4, CH50, and MCP-4
Phenotypic and functional changes from baseline in immune subsets using cytometric, genomic and/or proteomic analyses of cells harvested from endotracheal tubes, mini BAL and blood
Anti-SARS-CoV-2 T cell immunity
Anti-SARS-CoV-2 humoral immunity

11.12 Removal of Subjects from the Study

At any time, the investigator can remove a subject from the study or discontinue study drug dosing, if deemed necessary for the subject's safety. The Sponsor also reserves the right to terminate the study at any time. The reason for early treatment discontinuation and early withdrawal from the study will be collected in the eCRFs. Subjects who discontinue treatment early should continue to attend all Follow-up study visits unless they have withdrawn consent for any further follow-up.

If a subject requests or decides to withdraw consent from the study, all efforts will be made to complete and report the observations as thoroughly as possible up to the subject's date of study withdrawal.

11.13 Ventilator Procedures

Ventilator management, including weaning, shall follow the modified ARDS Network lower tidal volume (6 ml/kg PBW) protocol (Appendix A Ventilator Protocol). If not already being used, this low tidal volume protocol for mechanical ventilation shall be initiated within one hour of randomization. Since the time a subject achieves unassisted ventilation affects the co-primary endpoint, days free of ventilation, and because recent evidence-based consensus

recommendations have identified a best practice for weaning, weaning strategy will also be controlled by protocol rules in accordance with these evidence-based recommendations ([Appendix B Ventilator Weaning Procedure](#)). This will assure similar weaning methods and provide potential benefit to both study groups. This newer weaning strategy is a simplified version of the protocolized weaning strategy used in prior ARDS Network studies.

11.14 Assessment of Concomitant Medications

Reportable concomitant medications will be captured in the electronic database system as defined below based on timing of study drug administration. Medication doses can be reported as ranges and changes in dose can be reported if deemed clinically significant by the investigator.

Prior to study drug administration:

- Vaccine status
- COVID-specific therapies
- Immunosuppressive therapies (steroids, DMARDs, biologics)
- Antibiotics
- Vasopressors

Following study drug administration:

- COVID-specific therapies
- Immunosuppressive therapies
- Antibiotics
- Vasopressors
- Neuromuscular blockade
- Any treatment for an AE
- Changes in BP meds or addition of new meds (hypotension + hypoxemia)
- Change in oxygen/ventilator

12 ADVERSE EVENTS

An AE is defined as any unfavorable and unintended sign (including an abnormal laboratory finding), symptom, or disease or any worsening of a pre-existing condition temporally associated with the use of a study drug, whether or not related to study drug. From signing the ICF to study drug administration, all SAEs and nonserious AEs related to protocol-mandated procedures will be recorded on the SAE/AE eCRF. All other untoward medical occurrences observed during screening, including exacerbation or changes in the medical and surgical history will be captured on the medical and surgical history eCRF.

An AE that occurs before the first administration of the study drug will be considered a pre-treatment AE. A TEAE is defined as any adverse event that was not present before the first administration of the study drug, or any event already present, that worsens in either severity or frequency, following exposure to the study drug. AEs that occur after treatment with IP or during the Safety Follow-up Period will be documented on the AE eCRF. The investigator will assess AE severity, the causality relationship of the AE to study drug, and will treat the subject as medically required to ensure the subject's safety.

AEs will be captured through the EOS Visit at Day 56 or the ET Visit. Reportable adverse events are defined based on timing of study drug administration, as follows:

- Treatment – Day 7: AEs grade 3+ that are not expected to occur in critically ill patients, per the discretion of the investigator.
- Treatment Day 8 – Day84/EOT: AEs grade 4+ that are not expected to occur in critically ill patients, per the discretion of the investigator.

Events expected in the critically ill and are being captured in the eCRF should not be reported as adverse events unless considered to be related to the study drug or unexpectedly severe or frequent per the discretion of the investigator. These include but are not limited to; need for vasoactive drugs or fluids for hypotension, decreased PaO₂/FiO₂, transient hypoxemia, need for renal replacement therapy, or worsening acute respiratory distress syndrome.

Investigators should use their clinical judgment to determine whether a subject is to be withdrawn due to an AE. In the event the subject requests to withdraw from study-related treatment or the study due to an AE, the subject should be asked to return for all remaining study visits. In the event a subject is withdrawn from the study, an ET Visit should be completed. All subjects experiencing AEs, including clinically significant abnormal laboratory values, whether associated with the study drug, must be monitored until the condition (1) returns to normal, (2) returns to the subject's baseline, (3) the investigator determines the AE has reached a stable outcome and is no longer clinically significant, or (4) the subject is considered lost to follow-up.

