The Treatment Period will begin on Day 0 with randomization (Part 2 only) and administration of the investigational product (IP; cePolyTregs or placebo) and have a duration of 28 days. During the Treatment Period, subjects will be followed closely for outcomes to define the safety, tolerability, PD/biomarker changes, and efficacy of cePolyTregs. Subjects meeting clinical criteria for intra-hospital or inter-hospital transfer, as well as hospital discharge, will be followed according to the Schedule of Events (SOE) table irrespective of the location of the subject; ambulatory follow-up visits may be conducted at the study center or with in-home visiting study support staff. Following the Treatment Period, subjects will enter the Safety Follow-up Period.

Safety Follow-up Period

The Safety Follow-up Period will have a duration of 56 days, culminating with an end-of-study (EOS) visit on Day 84.

If subjects terminate early from the study for reasons other than death, they will be asked to undergo an Early Termination (ET) Visit within 7 days of their termination; the reasons for early termination will be documented. Since this is a single-dose study, subjects experiencing a product-related DLT will be asked to remain in the study and complete all study visits through the EOS visit. These subjects will not be replaced. If a subject terminates early for a reason other than a toxicity during the Treatment Period, the subject may be replaced at the discretion of the sponsor.

A DSMB will periodically convene and review all available clinical and laboratory data during the study. After its evaluation, the DSMB may recommend study continuation (with or without modification) or termination of a dose; the DSMB may also recommend de-escalation to a lower dose. If escalation is terminated, the next-lower dose may be declared the MTD and/or RP2D. Alternatively, an additional cohort at an intermediate dose may be added to better define the MTD and/or RP2D.

Dose Limiting Toxicity, Maximum Tolerated Dose, Dose Escalation Stopping Rules, and Individual Subject Stopping Rules:

A DLT is defined as any related TEAE of NCI CTCAE 5.0 grade ≥ 3 which also represents a shift from baseline clinical status of ≥ 1 NCI CTCAE grade.

The MTD is defined as the cePolyTregs dose below the dose at which 2 or more of 6 subjects receiving cePolyTregs in a Part 1 cohort experience a DLT, as confirmed by the DSMB.

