8 INVESTIGATIONAL PLAN

8.1 Overall Study Design and Plan

This is a Phase 1/2a study to evaluate the safety, tolerability, pharmacodynamics (PD), and efficacy of cePolyTregs in subjects with ARDS associated with SARS-CoV-2 infection. The study will be conducted in 2 parts. Part 1 is an open-label Phase 1 study to assess escalating doses of cePolyTregs administered as a single IV dose. Part 2 is a double-blind, randomized, placebo-controlled, parallel-group study of the Recommended Phase 2 Dose (RP2D) of a single IV dose of cePolyTregs compared to placebo. Part 1 will include up to 3 cohorts of 3 to 6 subjects/cohort followed for a total of 12 weeks. Part 2 will include 1 cohort of subjects receiving cePolyTregs and 1 cohort of subjects receiving placebo/standard of care (SOC) followed for a total of 12 weeks. Total study duration is up to 87 days for an individual subject

All subjects in both parts of the study will receive standard of care treatment for COVID-19, including dexamethasone per institutional guidelines and other approved therapies for ARDS associated with SARS-CoV-2 infection per institutional guidelines.

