8.1.3 Screening Period

The Screening Period will begin when the informed consent form (ICF) is signed. During this period, subjects will undergo baseline assessments to determine eligibility for study participation. The Screening Period duration will be up to 3 days but may be as short as is necessary to complete all screening evaluations; it will end after all evaluations required to meet eligibility have been completed. If a subject meets all eligibility criteria, they will be offered enrollment into the study.

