8.1.4 Treatment Period

The Treatment Period will begin on Day 0 with randomization (Part 2 only) and administration of the investigational product (IP; cePolyTregs or placebo) and have a duration of 28 days. During the Treatment Period, subjects will be followed closely for outcomes to define the safety, tolerability, PD/biomarker changes, and efficacy of cePolyTregs. Subjects meeting clinical criteria for intra-hospital or inter-hospital transfer, as well as hospital discharge, will be followed according to the Schedule of Events (SOE) table (Section [5.2](#)) irrespective of the location of the subject; ambulatory follow-up visits may be conducted at the study center or with in-home visiting study support staff. Following the Treatment Period, subjects will enter the Safety Follow-up Period.

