8.1.5 Safety Follow-up Period

The Safety Follow-up Period will have a duration of 56 days, culminating with an end-of-study (EOS) visit on Day 84.

If subjects terminate early from the study for reasons other than death, they will be asked to undergo an Early Termination (ET) Visit within 7 days of their termination; the reasons for early

termination will be documented. Since this is a single-dose study, subjects experiencing a product-related DLT will be asked to remain in the study and complete all study visits through the EOS visit. These subjects will not be replaced. If a subject terminates early for a reason other than a toxicity during the Treatment Period, the subject may be replaced at the discretion of the sponsor.

A DSMB will periodically convene and review all available clinical and laboratory data during the study. After its evaluation, the DSMB may recommend study continuation (with or without modification) or termination of a dose; the DSMB may also recommend de-escalation to a lower dose. If escalation is terminated, the next-lower dose may be declared the MTD and/or RP2D. Alternatively, an additional cohort at an intermediate dose may be added to better define the MTD and/or RP2D.

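### Protocol Section 12 ends adverse event capture at an end-of-study visit on Day 56, but the end-of-study visit is on Day 84; the passages conflict and need a one-line correction

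*Combined protocol and SAP*

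**What the plan says.** Section 12 (Adverse Events) gives the capture rule: "AEs will be captured through the EOS Visit at Day 56 or the ET Visit". It therefore does two things at once: it dates the EOS visit to Day 56 and ends AE capture there.

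Other parts of the protocol place the EOS visit four weeks later:

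- Section 8.1.5: "The Safety Follow-up Period will have a duration of 56 days, culminating with an end-of-study (EOS) visit on Day 84". The Synopsis uses the same date: "culminating with an end-of-study (EOS) visit on Day 84".
- Section 8.1 has subjects "followed for a total of 12 weeks" and adds: "Total study duration is up to 87 days for an individual subject".
- The Schedule of Events (Section 5.2) has Day 56 as an intermediate follow-up visit and Day 84 (or early termination) as the last column. The AE assessment row is marked at all 11 time points, including Day 84.

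Section 12 also disagrees with itself. The paragraph before the capture rule has AEs from the Safety Follow-up Period entered on the AE eCRF. The second reporting bullet after it covers Day 8 to "Day84/EOT: AEs grade 4+ that are not expected to occur in critically ill patients". The abbreviation list in Section 6 defines EOS and ET but not EOT.

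**The concern.** The sentence is the only one in the AE section that states outright when capture stops, so it is a natural source for eCRF windows, completion guidelines and site training. It also names a day on which a real visit takes place, so a site could apply it without noticing anything odd.

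Safety and tolerability is a primary objective of both parts (Section 8.5.1), related TEAEs of grade 3 or higher are a primary endpoint in Part 2 (Section 8.6.1), and TEAE, serious TEAE and AESI incidence is tabulated for the safety population (Section 13.6). Those tabulations presuppose one observation window. With up to 12 centers reading two different end dates, subjects could be observed for different lengths of time, and pooled incidence and the comparison of Part 1 cohorts would be harder to interpret.

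**Working it through.** **Inputs**

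- Screening: "The Screening Period duration will be up to 3 days" (Section 8.1.3).
- Treatment Period: starts on Day 0, "and have a duration of 28 days" (Section 8.1.4).
- Safety Follow-up Period: 56 days (Section 8.1.5).
- Stated AE capture end: Day 56 (Section 12).

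**Reproducing the protocol's own timeline**

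- EOS day = treatment + follow-up = 28 + 56 = Day 84, as stated.
- In weeks: 84 / 7 = 12, as stated.
- Maximum duration = 3 + 28 + 56 = 87 days, as stated.

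**Testing Day 56 as the EOS day**

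- Follow-up would be 56 / 7 = 8 weeks; the protocol says 12.
- The Safety Follow-up Period would last 56 − 28 = 28 days; the protocol says 56.
- Maximum duration would be 3 + 56 = 59 days; the protocol says 87.

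None of the three agrees with the protocol, and no other passage supports Day 56 as the EOS visit.

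**Calendar time outside the literal capture window**

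- 84 − 56 = 28 days.
- As a share of post-dose time (Day 0 to 84): 28 / 84 = 33%.
- As a share of the defined Safety Follow-up Period (Day 28 to 84): 28 / 56 = 50%.

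**Which events on Days 57 to 84 depend on the sentence**

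- SAEs: Section 12.6.2 requires all of them within 24 hours and states no Day 56 limit. Not dependent.
- AESIs, including respiratory infections that need treatment: Section 12.2 requires AE and AESI eCRFs within 24 hours even when nonserious, again with no Day 56 limit. They would be lost only if a site carried the Section 12 cut-off over to them.
- Deaths: all-cause mortality is assessed at Day 84 (Section 8.6.3) and the DSMB reviews every death (Section 8.8.6). Not dependent.
- Unexpected events of grade 4 or higher, the reportable class from Day 8: many would also be SAEs, since the fallback scale in Section 12.4 describes grade 4 as life-threatening or disabling and Section 12.1 makes a life-threatening event serious. The nonserious remainder, such as some grade 4 laboratory values, is dependent.
- Events expected in critical illness but judged drug-related, or unusually severe or frequent: reportable, with no grade floor attached to that exception. The nonserious ones, which may be of lower grade, are dependent.

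**The case against.** The strongest reply is that this is a drafting slip which the surrounding text largely corrects. The rule points to the EOS visit, which is dated Day 84 elsewhere; the paragraph before it covers the Safety Follow-up Period; the bullet after it runs to Day 84; and AE assessment is scheduled at Day 84. A site would have to disregard all of these to stop at Day 56, and the eCRF is not among the documents, so no wrongly set window has been shown. That stands as an argument about likelihood. It does not make the sentence correct, and nothing tells a site which line governs.

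A reader might go further and infer that the last third of the safety data, late infections included, will be lost. The documents do not support that. One third is a share of calendar days and says nothing directly about events. The reporting rules above keep SAEs, AESIs and deaths in view, and product exposure is expected to last about 2 weeks (Section 8.1.1). Nor would all 118 subjects still be at risk on Day 57: taking the 50% anticipated mortality in Section 8.8.6 at face value, about 0.5 × 118 = 59 would be.

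A reader might also infer bias between the Part 2 arms. That is unlikely: randomization is stratified by site, so a site-level difference in cut-off should fall on both arms about equally, and the primary safety analysis is descriptive with no formal comparison (Section 13.1). Part 1 escalation rests on a 7-day DLT period, which a Day 56 cut-off does not touch.

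**Conclusion.** The Section 12 sentence is wrong on the protocol's own timeline and should be corrected. It is an internal inconsistency in an operative rule. Whether it arose from mistaking the 56-day follow-up length for a study day cannot be told from the documents.

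Applied literally, it removes 28 days from AE capture: 33% of post-dose time, or 50% of the Safety Follow-up Period. The practical exposure is narrower and consists mainly of nonserious reportable events on Days 57 to 84: nonserious unexpected grade 4 events, lower-grade events judged drug-related and, if sites apply the cut-off to them, nonserious AESIs. The documents give no late event rates, so the number of events cannot be estimated.

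This assessment assumes that sites follow Sections 12.2 and 12.6.2 as written through Day 84. The remaining reason to act is that the window for primary safety data is ambiguous across up to 12 centers.

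**What to change.** - In the Section 12 capture sentence, change Day 56 to Day 84 and leave the early-termination alternative as it is. This matches the Synopsis, Section 8.1.5 and the Schedule of Events.
- In the second reporting bullet, replace the undefined EOT so that the window ends at Day 84 (EOS) or ET.
- Confirm that the AE window in the eCRF and its completion guidelines runs to Day 84 for every subject.

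The cost is two small text edits and one eCRF check. No visit, assessment or clinical rule changes, because AE assessment at Day 84 is already scheduled.

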8.6 Endpoints

8.6.1 Primary Endpoints

Part 1 (Phase 1):

Safety and tolerability of cePolyTregs as assessed by DLTs, defined as any related treatment-emergent adverse event (TEAE) with an NCI CTCAE 5.0 grade ≥ 3 which also represents a shift from baseline clinical status of ≥ 1 NCI CTCAE grade.

Part 2 (Phase 2a):

Efficacy of cePolyTregs compared with placebo/SOC, as assessed by time to recovery, defined as the first day during the 28 days after randomization on which a subject meets the criteria for category 0, 1, 2, 3, or 4 on the WHO severity scale for COVID-19 pulmonary syndrome.

Safety of cePolyTregs as assessed by the occurrence of related TEAEs with an NCI CTCAE 5.0 grade ≥ 3 .

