8.8.2 Maximum Tolerated Dose

The MTD is defined as the cePolyTregs dose below the dose at which 2 or more of 6 subjects receiving cePolyTregs in a Part 1 cohort experience a DLT, as confirmed by the DSMB.

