8.8.3 Dose-Limiting Toxicities

A DLT is defined as any related TEAE \geq NCI CTCAE 5.0 Grade 3 in a subject who has received treatment with cePolyTregs which also represents a shift from baseline clinical status of \geq 1 NCI CTCAE grade.

Adverse events related to the standard of care (e.g., dexamethasone) are not considered DLTs. TEAEs related to ARDS will not be considered DLTs, unless they are judged to be related (or also related) to cePolyTregs.

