12.2 Adverse Events of Special Interest

To date, there have been no clinical studies using cePolyTregs, and nonclinical studies with autologous, homologous products have not demonstrated specific toxicities related to administration of adoptively transferred Tregs. Potential adverse events of interest in the COVID-19 setting based on the biology of cePolyTregs include infusion/hypersensitivity reactions and infections including pneumonia and those involving pathogens not anticipated in a COVID-19 setting; these clinical parameters will be closely monitored in the current study.

The following events are defined as AESIs that should be reported by completing the Adverse Event eCRF and AESI eCRFs within 24 hours of the site's awareness of them, even if they do not meet criteria for an SAE:

- Evidence of hypersensitivity or transfusion incompatibility (e.g. new rash, urticaria, new onset bronchospasm).
- Diagnostically or clinically confirmed respiratory infections that were not present before study drug infusion AND that require a treatment course with antimicrobial agents, operative management, or procedural drainage.
- Within 6 hours of IP exposure:
 - New ventricular tachycardia, ventricular fibrillation, or asystole or any cardiac arrhythmia requiring cardioversion.
 - Hypoxemia requiring an increase in FiO₂ of 0.2 or more and/or an increase in PEEP of 5 cm H₂O or more to maintain SpO₂ in the target range of 88–95%, for a sustained duration (>2 hours) and not associated with a care procedure.

- Pulmonary Embolism

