12.6 Reporting Adverse Events

12.6.1 Reporting Procedures for Nonserious Adverse Events

The investigator is responsible for ensuring that all reportable AEs observed by the investigator or designee or reported by the subject are reported using the AE eCRF.

The investigator will assign the following AE attributes:

- AE diagnosis or syndrome(s), if known (if not known, signs or symptoms)
- Dates of onset and resolution (if resolved)
- Severity
- Causality relationship to study drug or study-related procedures
- Action taken
- Outcome

Follow-up of nonserious AEs will continue through the last day on the study and/or until a definitive outcome (e.g., resolved, resolved with sequelae, lost to follow-up) is achieved.

When a subject is withdrawn from the study because of a nonserious AE, the Sponsor and/or designee must be notified by email or phone within 48 hours.

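### From Day 8 the reportable-event list in Section 12 leaves out a small class of related grade 3 events that the Part 2 primary safety endpoint counts, and it conflicts with other recording instructions in the protocol

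*Combined protocol and SAP*

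**What the plan says.** All references are to the combined protocol and SAP.

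**Endpoint.** Section 8.6.1 gives the Part 2 primary safety endpoint as "Safety of cePolyTregs as assessed by the occurrence of related TEAEs with an NCI CTCAE 5.0 grade" 3 or higher. It states no time window.

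**Reporting list.** Section 12 makes unexpected events of grade 3 or higher reportable from treatment to Day 7. From Day 8 the line runs to "Day84/EOT: AEs grade 4+ that are not expected to occur in critically ill patients, per the discretion of the investigator". Events that are expected in the critically ill, and captured elsewhere in the eCRF, "should not be reported as adverse events unless considered to be related to the study drug or unexpectedly severe or frequent".

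**Duty to report.** Under Section 12.6.1 the investigator must ensure that "all reportable AEs observed by the investigator or designee or reported by the subject are reported using the AE eCRF". That ties the form to the list.

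**Text that points the other way.** Earlier in Section 12: "AEs that occur after treatment with IP or during the Safety Follow-up Period will be documented on the AE eCRF". That sentence has no grade limit.

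**Part 1.** Section 8.8.3 begins "A DLT is defined as any related TEAE" and goes on to require grade 3 or higher with a shift of at least one grade. The definition carries no window, but the synopsis and Sections 8.1.1 and 8.8.1 refer to a 7-day DLT assessment period when they describe escalation decisions.

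**The concern.** A reporting rule should be at least as wide as the endpoint that it feeds. Here it is narrower after Day 7, and the omission falls in an odd place. Read literally, a familiar ICU complication that the investigator attributes to the cells is reported. An unusual grade 3 event with the same attribution is not, although it would be the more informative safety signal.

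The protocol also gives two instructions on the same matter. With up to 12 centers, some may follow the list and others the general sentence about the AE eCRF, so recorded rates could depend partly on site practice. The product has had no earlier clinical study (Section 8.2), and its expected exposure of about two weeks (Section 8.1.1) extends past the Day 7 cut.

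**Working it through.** The plan states no figure on this point, so the check compares texts and then sizes one missed event.

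**1. A related grade 3 event that is not serious and not an AESI, taken through Section 12**

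| Event | Treatment to Day 7 | Day 8 to Day 84 | In the Part 2 endpoint? |
|---|---|---|---|
| Expected in critical illness | Reportable, by the related-event exception | Reportable, by the same exception (it has no day limit) | Yes |
| Not expected | Reportable, by the list (grade 3+) | Not on the list (grade 4+ only) | Yes |

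The mismatch is confined to one cell: unexpected events from Day 8.

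**2. Routes that take events out of that cell**
- All SAEs are reported whatever their cause (Section 12.6.2). Section 12.1 includes prolonged hospitalization and important medical events. For events outside CTCAE, Section 12.4 describes grade 3 in terms of hospitalization or invasive intervention. Many grade 3 events will therefore be serious.
- AESIs are reported whether or not they are serious (Section 12.2). For infections, that list covers "Diagnostically or clinically confirmed respiratory infections that were not present before study drug infusion AND that require a treatment course", whereas Section 8.6.2 also names infections with unanticipated pathogens, without restriction to the lung. A non-respiratory infection on Day 10, graded 3, judged related and not serious, could miss both routes. In this population such an infection would often be serious.

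**3. Other instructions that call for recording**
- Section 11.3: treatment-emergent examination findings of clinical significance are recorded as AEs.
- Section 11.5: the same for ECG findings.
- Section 12.3: laboratory changes that need treatment or a change of therapy count as AEs. Section 13.6 grades all gradable laboratory parameters.
- Section 14.7: progress notes record the severity of any AE and the relatedness assessment, and AEs are entered in the database.

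None of these has a grade cut or a Day 8 cut. They make the class smaller and deepen the conflict with the list.

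**4. Timing, from the schedule of events**
- Scheduled post-dose AE assessments: Days 0.5, 4, 7, 14, 21, 28, 42, 56 and 84, which is 9. Those after Day 7: 6. Share: 6/9 = 67%.
- Days of expected exposure under the grade 3 rule: 7/14 = 50%.

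These are calendar fractions, not shares of missed events. Assessment is also daily while a subject is in hospital.

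**5. Effect of one missed subject**
- Part 2 arm of 50: 1/50 = 0.02, or 2 percentage points for each subject whose only qualifying event is not recorded.
- Part 1 cohort, only if a DLT can occur after Day 7: 1/6 = 17 points to 1/3 = 33 points.

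The documents give no rate of late related grade 3 events, so an expected number missed cannot be derived. With no such events there is no effect.

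**The case against.** The best defence is that most of the protocol already asks for these events. The general sentence in Section 12, the rules for examinations, ECGs and laboratory values, and the source-note requirement all point to recording, and the SAE and AESI routes take the more serious cases. An event missing from the AE form might also be recovered from progress notes. This stands as a limit on size. It does not remove the conflict: Section 12.6.1 refers to reportable events, and the list is the only text that says which events those are.

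A reader might infer that both primary safety endpoints are under-captured. The documents do not settle that. The synopsis and Sections 8.1.1 and 8.8.1 name a 7-day DLT assessment period, and the grade 3 rule in Section 12 ends on the same day. If DLTs are meant to end at Day 7, the Part 1 endpoint is untouched. The definitions in Sections 8.6.1 and 8.8.3 do not state that limit, so the Part 1 effect is conditional.

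A reader might also infer an escalation defect: late DLTs could bring a cleared cohort to two while the next dose is being given, with no written pause. That needs the no-window reading. Even then, Section 8.8.2 sets the MTD below a dose at which "2 or more of 6 subjects receiving cePolyTregs in a Part 1 cohort experience a DLT, as confirmed by the DSMB". Section 8.7 calls for a DSMB opinion, and Sections 8.1.5 and 8.8.1 let the board recommend ending a dose, de-escalating or stopping. The DSMB Charter is not among the documents and may add a pause. An automatic pause is a preference, not the repair of a shown error.

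**Conclusion.** The point holds for the Part 2 primary safety endpoint. From Day 8 the list is narrower than the endpoint for related, unexpected grade 3 events that are neither serious nor AESIs. Because it conflicts with other recording instructions, such events may be recorded at some sites and not at others, and the endpoint may be under-counted. The text does not support saying that they will be lost.

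The size is small and not known: 2 percentage points of an arm's proportion per subject missed, with no rate in the documents to say how many. Section 13.1 makes this endpoint descriptive with no formal comparison between arms, so no test or error rate is affected; what is at risk is the completeness of the reported proportion.

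The conclusion assumes that sites treat the list as the definition of a reportable event, and that the Part 2 endpoint runs past Day 7, as its unlimited wording implies. The same effect on Part 1 needs the further assumption that DLTs are not confined to 7 days. No escalation error is shown.

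**What to change.** In Section 12, add to the Day 8 to Day 84 line: *and any grade 3+ event judged related to study drug*. The list then covers what Section 8.6.1 counts and no longer conflicts, for these events, with the general documentation sentence.

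The cost is one clause and a small amount of extra AE reporting: related grade 3 events from Day 8 in up to 118 subjects (18 + 100). AE assessments are already scheduled at all six later visits and done daily in hospital, so no visit or procedure is added. The 7-day escalation timing and Section 8.7 stay as they are.
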